## 8 CLINICAL TRIAL SITE

### 8.1 SITE/INVESTIGATOR INCLUSION CRITERIA

The Principal Investigator, [name] (Imperial Clinical Research Facility, Hammersmith Hospital) is experienced in Phase I clinical trials. Participants will be seen by clinical staff from the Imperial Clinical Research Facility, Imperial College Healthcare NHS Trust, who have experience of running Phase 1 vaccine trials.

### 8.2 CI'S QUALIFICATIONS & AGREEMENTS

1. The investigator should be qualified by education, training, and experience to assume responsibility for the proper conduct of the trial at their site and should provide evidence of such qualifications through an up-to-date curriculum vitae and/or other relevant documentation requested by the Sponsor, the REC and/or the regulatory authorities.
2. The investigator should be thoroughly familiar with the appropriate use of the investigational product(s), as described in the protocol, in the current Investigator Brochures, in the product information and in other information sources provided by the Coordinating Centre.
3. The investigator should be aware of, and should comply with, the principles of ICH GCP and the applicable regulatory requirements. A record of GCP training should be accessible for all investigators.
4. The investigator/site should permit monitoring and auditing by the Sponsor, and inspection by the appropriate regulatory authority(ies)
5. The investigator should maintain a delegation log of appropriately-qualified persons to whom the investigator has delegated significant trial-related duties.
6. The investigator should sign an investigator statement, which verifies that the site is willing and able to comply with the requirements of the trial.

### 8.3 ADEQUATE RESOURCES

1. The investigator should be able to demonstrate a potential for recruiting the required number of suitable subjects within the agreed recruitment period.
2. The investigator should have sufficient time to properly conduct and complete the trial within the agreed trial period.
3. The investigator should have available an adequate number of qualified staff and adequate facilities for the foreseen duration of the trial to conduct the trial properly and safely.
4. The investigator should ensure that all persons assisting with the trial are adequately informed about the protocol, the investigational product(s), and their trial-related

duties and functions.

5. The site should have sufficient data management resources to allow prompt data entry into the CRF. Sites that have previously participated in trials coordinated by the same centre should have a proven track record of timely data entry.

#### **8.4 SITE ASSESSMENT**

In addition and in compliance with the principles of ICH GCP, all site staff participating in the trial must complete the Signature and Delegation of Responsibilities Log and forward this to the Coordinating Centre. An up-to-date copy of this log must be stored in the trial master file at the Coordinating Centre and the Investigator Site File (ISF) at the Site.

## 9 SELECTION OF PARTICIPANTS

The eligibility criteria for this trial have been carefully considered. There will be **no exceptions** to eligibility requirements at the time of randomisation. The eligibility criteria are the standards used to ensure that only medically appropriate participants are considered for this study. Participants not meeting the criteria will not be permitted to join the study. For the safety of the participants, as well as to ensure that the results of this study can be useful for making treatment decisions regarding other individuals as well as scientific conclusions, it is important that no exceptions be made to these admission criteria.

Participants will be considered eligible for enrolment in this trial if they fulfil all the inclusion criteria and none of the exclusion criteria as defined below.

### 9.1 PARTICIPANT INCLUSION CRITERIA

1. Men and women aged between 18 and 50 years on the day of screening
2. BMI between 18-30
3. Seronegative for Adenovirus 4 serum neutralising antibodies
4. Available for follow-up for the duration of the study
5. Willing and able to give written informed consent
6. At low risk of HIV infection and willing to remain so for the duration of the study defined as:
  - no history of injecting drug use in the previous ten years
  - no gonorrhoea or syphilis in the last six months
  - no high risk partner (e.g. injecting drug use, HIV positive partner) either currently or within the past six months
  - no unprotected anal or vaginal intercourse in the last six months, outside a relationship with a regular partner known to be HIV negative
7. Willing to undergo HIV testing
8. Willing to undergo a STI screen for chlamydia, gonorrhoea and syphilis
9. Must agree to require male sexual partner to use condoms, from at least 14 days before the first vaccination until at least 4 months after the last
10. If heterosexually active female capable of becoming pregnant, must (in addition to requiring male partner to use condoms) agree to use hormonal contraception, or to complete abstinence, from at least 30 days before the first vaccination until at least 4 months after the last. [Note: Acceptable hormonal contraception is combined (estrogen and progestogen containing) or progestogen-only hormonal contraception associated with inhibition of ovulation. Complete abstinence can be used, when in line with the preferred and usual lifestyle of the subject. Periodic abstinence (calendar, symptothermal, post-ovulation methods), withdrawal (coitus interruptus), spermicides only, lactational amenorrhoea method, and IUD/IUS are not acceptable methods of contraception.]
11. If sexually active male, must agree to use condoms from the day of first vaccination until at least 4 months after the last. [Note: Additional use of an effective method of contraception is recommended for any non-pregnant female partner over the same period.]
12. Agree to abstain from donating blood, eggs or sperm from the day of first vaccination until at least 3 months after the end of their participation in the trial

13. Registered with a GP for at least the past month
14. Entered and clearance obtained from The Overvolunteering Prevention System (TOPS) database

*Participants will be advised that they cannot enrol in any other trials of medicinal products during the period from screening to the final visit in Ad4HIV. All participants will be entered onto the TOPS database as a measure to prevent over volunteering. If staff discover that a participant is enrolled on another study during this period, they must immediately contact the Principal Investigator for advice. Decisions will be reviewed on a case by case basis and participant safety will be the primary concern*

## 9.2 PARTICIPANT EXCLUSION CRITERIA

1. Are pregnant or breast feeding, or living with anyone under the age of 5 years old or over 75 years old
2. Have close contact with an immunocompromised individual thought to be at clinical risk from Adenovirus infection
3. Clinically relevant abnormality on history or examination including:
  - a. Liver disease with inadequate hepatic function
  - b. Any skin condition which may interfere with the trial assessment of the injection sites
  - c. Haematological, metabolic, gastrointestinal or cardio-pulmonary disorders
  - d. Uncontrolled infection; autoimmune disease, immunodeficiency
4. Known hypersensitivity to any component of the vaccine formulations used in this trial, or have severe or multiple allergies to drugs or pharmaceutical agents
5. History of severe local or general reaction to vaccination defined as
  - Local: extensive, indurated redness and swelling involving most of the antero-lateral thigh or the arm, not resolving within 72 hours
  - General: fever  $\geq 39.5^{\circ}\text{C}$  within 48 hours; anaphylaxis; bronchospasm; laryngeal oedema; collapse; convulsions or encephalopathy within 72 hours
6. Receipt of live attenuated vaccine within 60 days or other vaccine within 30 days of enrolment
7. Receipt of an experimental vaccines containing HIV antigens, Ad4 and MVA-C products at any time in the past
8. Receipt of blood products or immunoglobulin within 4 months of screening, or drugs that suppress the immune system, such as steroids (including inhaled steroids, excluding topical steroids unless applied to the upper arm), in the preceding 3 months
9. Participating in another trial of a medicinal product, completed less than 30 days prior to enrolment
10. HIV 1 or 2 positive or indeterminate on screening
11. Positive for antibodies to hepatitis B surface antigen, hepatitis C antibody or serology indicating active syphilis requiring treatment
12. Clinically significant positive reaction in antinuclear antibody screen or clinically significant immunoglobulin (IgA, IgG or IgM) values
13. Grade 1 or above clinically significant routine laboratory parameters
14. Unable to read and/or speak English to a fluency level adequate for the full comprehension of procedures required in participation and consent

15. Women with a history of toxic shock syndrome
16. Women using an intrauterine device for contraception (as incompatible with softcup sampling)
17. Any other significant disease, disorder or finding which may significantly increase the risk to the volunteer because of participation in the study, affect the ability of the volunteer to participate in the study or impair interpretation of the study data
18. Unlikely to comply with protocol

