## 4 TRIAL ASSESSMENT SCHEDULE

TABLE 2 - SCHEDULE OF VISITS, IMMUNISATIONS AND ASSESSMENTS - PART 1 & PART 2

Visit		1	2	3	4	5	6	7	8	9	10	11
Study Month		M0			M3			M6				M12
Study Week		W0	W1	W4	W12	W13	W16	W24	W25	W26	W28	W48
Study Day		D0	D7	D28	D84	D91	D112	D168	D175	D182	D196	D336
Visit Windows (Days)	-90		±1	±2	(1) -7/+14	±1	±2	(1) -7/+14	±1	±2	±2	±14
Immunizations		X			X			X				
Informed consent	X											
Medical history/ demographics	X											
General physical examination	X											
Entry screen for Ad4 neutralising antibodies	X											
Symptom directed physical exam		X	X	X	X	X	X	X	X	X	X	
Concomitant medications	X	X	X	X	X	X	X	X	X	X	X	
Vital signs	X	X 	X		X 	X		X 	X	X	X	
Inspection of administration sites (I.M)	X				X 	X		X 	X			
Solicited Adverse Events		X 	X		X 	X		X 	X			
Review Solicited AE on diary card			X			X			X			
Unsolicited Adverse events		X 	X	X	X 	X	X	X 	X	X	X	
Serious adverse events		X	X	X	X	X	X	X	X	X	X	X
Urine pregnancy test (women) 	X	X			X			X				X
Routine safety bloods 	X	X	X		X	X		X	X	X	X	
Antinuclear antibody and immunoglobulin  tests	X											
HIV test 	X	(X)	(X)	(X)	(X)	(X)	(X)	(X)	(X)	(X)	(X)	X
HBV, HCV and syphilis tests	X											
STI screen 	X											
Blood for serum – Immunogenicity		X		X	X		X	X	X	X	X	X
Blood for PBMC – Immunogenicity		X		X	X		X	X	X	X	X	X
Blood for PBMC – Infectivity		X		X			X		X	X	X	X
Mucosal antibody responses (rectal / genital / nasal)		X		X	X		X	X		X		X
Rectal swab for Ad4-EnvCN54 PCR		X	X	X		X	X		X	X	X	X
Rectal biopsies (optional; Part 2 only)		X 								X 		X 

 The second and third vaccinations (visits 4 and 7) can be shifted by -7 or up to +14 days. Subsequent visits would be shifted by the same number of days to ensure the interval to subsequent visits is maintained

 Confirmed negative prior to vaccination

 The parameters are detailed in section 12.3.3

 HIV testing at additional time points may be performed upon request of the volunteer and principal investigator or designee as medical or social circumstances warrant

 Genital swabs or urine for *Neisseria gonorrhoea* and *chlamydia trachomatis* will be collected

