#### 12.1.3 HIV RISK ASSESSMENT & SEROLOGY TESTING

An HIV risk assessment will be performed according to the relevant eligibility criterion.

The following will be collected from all participants:

- Serology for HIV and syphilis
- Serology for markers of hepatitis B and hepatitis C infection
- Urine for Chlamydia and gonorrhoea at screening
- Serology for Ad4 neutralising antibodies
- Serology for antinuclear antibodies and immunoglobulins IgA, IgG and IgM

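### Exclusion 11 turns on antibody to hepatitis B surface antigen, a marker of immunity, while section 12.1.3 screens for markers of infection and Table 2 names no marker

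*Protocol*

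**What the plan says.** Protocol section 9.2, item 11, excludes a volunteer who is "Positive for antibodies to hepatitis B surface antigen, hepatitis C antibody or serology indicating active syphilis requiring treatment". Surface antigen appears there only as the target of the antibody. The excluding hepatitis B result is the antibody.

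The screening procedures are worded differently. Section 12.1.3 lists "Serology for markers of hepatitis B and hepatitis C infection" among the tests for all participants. Table 2 in section 4 has a single row at screening, "HBV, HCV and syphilis tests". Neither place names a hepatitis B marker. No section makes a positive surface-antigen result an exclusion, and none exempts antibody that comes from vaccination.

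Section 9 sets how strictly the list applies: "it is important that no exceptions be made to these admission criteria".

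Four other exclusions in section 9.2 could bear on a person with hepatitis B:
- 3a, found on history or examination: "Liver disease with inadequate hepatic function"
- 3d, found on history or examination: "Uncontrolled infection; autoimmune disease, immunodeficiency"
- 13: "Grade 1 or above clinically significant routine laboratory parameters"
- 17, in part: "Any other significant disease, disorder or finding which may significantly increase the risk to the volunteer because of participation in the study"

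None of the four names hepatitis B.

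**The concern.** The antibody and the antigen answer opposite questions. Antibody to surface antigen indicates that a person has been vaccinated or has cleared an infection. The antigen indicates that infection is present now. This is general serology; the protocol does not state it.

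A criterion that excludes on the antibody can therefore fail in two ways. It rejects healthy people because they are immune, and it does not act on an infected person who has no antibody. The first costs recruitment in a study that section 7.8 says may be hard to recruit to because its schedules are complex. The second matters for safety. Depending on group, participants receive a replicating adenovirus vector, MVA or adjuvanted protein, and ALT and bilirubin are graded safety parameters in Appendix 1. Liver disease that was present at entry could be mistaken for a vaccine effect.

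**Working it through.** No arithmetic applies, and the plan gives no figure on this point. The check sets the texts side by side and applies item 11 as written.

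**Step 1: which marker each place names**

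| Place | Hepatitis B wording | Marker named |
|---|---|---|
| 9.2, item 11 | antibody to surface antigen | the antibody |
| 12.1.3 | markers of infection | none |
| Table 2 | HBV test | none |

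The only place that names a marker names the antibody, which vaccination alone can produce. The section that describes the screen refers to infection.

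**Step 2: item 11 applied literally**

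| Volunteer | Antigen | Antibody | Excluded by item 11? |
|---|---|---|---|
| Vaccinated, never infected | negative | positive | yes |
| Infection cleared, immune | negative | positive | yes |
| Neither vaccinated nor infected | negative | negative | no |
| Current carrier without the antibody | positive | negative | no |

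The first and last rows are the problem.

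**Step 3: does any other text make past hepatitis B vaccination a reason to exclude?** No. Exclusion 6 limits only recent vaccination (60 days for live attenuated, 30 days for other vaccines). Exclusion 7 concerns experimental HIV-antigen, Ad4 and MVA-C products. No rationale is given for rejecting people immune to hepatitis B.

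**Step 4: can the site correct the first row?** No. Admitting an antibody-positive volunteer would waive a written criterion, which section 9 forbids. Section 16.3 has monitors check adherence to the criteria.

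**Step 5: can the site still keep out the carrier in the last row?** Often, yes.
- 3a applies if hepatic function is inadequate.
- 3d applies if infection is uncontrolled.
- 13 applies if routine values, which under section 12.1.4 include ALT, alkaline phosphatase and bilirubin, are clinically significantly abnormal.
- 17 applies if the reviewing physician judges that the finding raises risk or impairs interpretation of the data.

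Using any of these adds an exclusion and waives nothing, so the no-exceptions rule does not stand in the way. The person not explicitly barred is a carrier who is well, has normal laboratory values, and is either not identified or not judged to fall under 17.

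**Step 6: drafting evidence.** Read strictly, the opening of item 11 also governs its hepatitis C part, giving antibodies to an antibody. The other two conditions in the item are aimed at infection. Both points suggest that antigen and antibody were mixed up in drafting. They do not change what the rule literally says.

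**The case against.** The strongest reply is that this is a slip any experienced physician would read through. Section 12.1.3 points to infection markers, nothing shows that the site tested only for the antibody, the section 2 summary lists significant acute or chronic disease as a principal exclusion, and section 9.4 requires a physician to sign off eligibility. Much of this stands, and it limits the point in several ways.

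- A reader might infer that carriers would be enrolled, or that the investigator is powerless to prevent it. The documents do not support this. A detected carrier can be excluded under 17 without any exception. The no-exceptions rule binds only on the over-exclusion side.
- A reader might infer that item 11 flatly contradicts a stated purpose. Section 12.1.3 describes the screen; it does not set out the aim of item 11. What is shown is that three places fail to name one consistent marker.
- A reader might picture every participant receiving all products and a biopsy. Only groups F to H receive Ad4, MVA and protein. Groups A to D receive no MVA, and A and E receive no Ad4. Biopsy is optional and confined to Part 2.
- A reader might want a count. If a share p of otherwise eligible volunteers carried the antibody, enrolling 60 would mean rejecting 60p/(1−p): about 7 at an assumed 10%, and 40 at an assumed 40%. Nothing in the documents places p in that range, so the count only restates the assumption.

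The reply does not remove the defect. Reading through item 11 to a presumed antigen test means that each antibody-positive volunteer enrolled breaches a written, mandatory criterion. Following it literally turns immune healthy people away.

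**Conclusion.** The point holds as an error in an operative eligibility rule, at moderate severity. As written, item 11 excludes on a marker of immunity, section 12.1.3 describes a screen for infection, and Table 2 is silent. The certain consequence of the literal text is that healthy volunteers with vaccine-induced antibody are rejected and the site cannot waive this. The safety consequence is narrower: item 11 does not itself bar an antibody-negative carrier, and after the other exclusions the gap is a well carrier with normal results. Such people should be rare in a healthy, low-risk population, but that is a judgement, not a figure from the protocol.

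The conclusion rests on the literal wording and on the general meaning of the two serological markers. The number of volunteers affected in either direction cannot be derived. Sample size, error rate and planned analyses are unaffected.

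**What to change.** Reconcile exclusion 11, section 12.1.3 and Table 2 so that all three name the same hepatitis B test and the same excluding result, one that marks current infection, in line with how 12.1.3 describes the screen. The wording suggests that surface antigen was meant; the sponsor should confirm this.

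The cost is a short protocol amendment. Hepatitis B serology is already taken at screening, so no visit or sample is added.

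The SAP is signed in July 2021 and refers to trial conduct in the past tense, so enrolment may be closed. In that case, the clinical study report should state which marker was actually tested and applied, and list any participant whose enrolment departed from item 11 as written. The report should also say whether any such departure was classed as a major deviation, because the per-protocol population (Protocol 14.5.1, SAP section 9) requires that there be none. The documents do not show that any such case arose.

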### **9.3 NUMBER & SOURCE OF PARTICIPANTS**

Forty eight healthy participants for Part 1, plus an additional 12 healthy participants for Part 2 will mainly be recruited through advertising, and through the investigator site's healthy volunteer database, and given contact details. They will be provided with further information about the study and asked to complete a short interview (by telephone or in person) to assess their suitability. They will be given or sent an information sheet.

### **9.4 SCREENING PROCEDURES & PRE-ENROLMENT INVESTIGATIONS**

Written informed consent must be obtained from participants after explanation of the aims, methods, benefits and potential hazards of the trial and **BEFORE** any trial-specific procedures are performed or any blood is taken for the trial. Participants should be given a minimum of 24 hours after receiving the information sheet to sign a consent form. It must be made completely and unambiguously clear that the participant is free to refuse to participate in all or any aspect of the trial, at any time and for any reason, without affecting their treatment.

At the screening visit the volunteer will be allocated a Trial ID. The trial will be discussed in detail, and any questions about the study will be answered. If participants are willing and interested they will be asked to sign the informed consent form.

Signed consent forms must be kept by the investigator and documented in the medical notes and case report form (CRF) and a copy given to the participant.

After written informed consent has been collected, assessments and investigations will be undertaken according to the schedule in Table 2. These include demographic, sexual and medical histories, general examination, and collection of urine and blood samples for routine laboratory investigations. Samples for tests for sexually transmitted infections including HIV will be collected. As soon as the required test results are available, data will be entered into the CRF and medical notes and the results of the screening investigations will be reviewed and eligibility signed off by a physician.

## 10 REGISTRATION & DISTRIBUTION INTO TREATMENT GROUPS

### 10.1 RANDOMISATION PRACTICALITIES

#### 10.1.1 PART 1

The enrolment visit will take place within 90 days after the screening visit and will be the same day as the first vaccination. Assessments and procedures will be undertaken according to the schedules in Table 2, and data entered on the CRF.

The study will use sentinel dosing as a safety precaution. The first 6 participants successfully enrolled into the trial will be sequentially pre-allocated to treatment groups B, C, D, F, G and H. The first participant will be enrolled to group B. The safety data for this participant will be reviewed at day 7 before enrolling the next participant to group C. This process will be repeated for the other groups. This will ensure an escalation of the number of Ad4-EnvCN54 administrations combined with either CN54gp140 protein boosts (B-D) or co-administered CN54gp140 and MVA-CN54 (F-H).

After the accumulated safety data (up to day 7) for the 6th participant has been reviewed, on their first day of dosing the remaining participants will be block randomised into groups as follows:

- Block 1 (n=10): A, A, B, C, D, E, E, F, G, H
- Blocks 2-6 (n=8/block): A, B, C, D, E, F, G, H

#### 10.1.2 PART 2

Six additional healthy participants per group will be recruited and randomised to the best two regimes from A-D (Ad4-EnvCN54/CN54gp140) and E-H (Ad4-EnvCN54/MVA-CN54/CN54gp140). The visits schedule for participants in Part 2 will be the same as that for participants in Part 1. Assessments and procedures will be undertaken according to the schedules in Table 2, and data entered on the CRF.

#### 10.1.3 PASS CRITERION FOR PART 2

The group selection for Part 2 is based on results generated from the primary immunogenicity endpoint (Week 26, Visit 9). In the event that more than one group has the same number of responders, mucosal antibody titre will be used to rank groups to determine which to take forward to Part 2. Should mucosal titers be indistinguishable between groups, then serum antibody levels will be taken into consideration in the selection of groups to progress to Part 2. The criterion for a positive mucosal response, and methods for ranking groups on the basis of mucosal and serum antibody titers, will be specified in the LAP. If any groups are associated with unacceptable product related adverse events, they will be discontinued from further study.

